5.2.1.2 Dose Modification

Adverse events (both non-serious and serious) associated with pembrolizumab exposure may represent an immunologic etiology. These adverse events may occur shortly after the first dose or several months after the last dose of treatment. Pembrolizumab must be withheld for drug-related toxicities and severe or life-threatening AEs as per Table 3 below. See Section 5.4 and Events of Clinical Interest Guidance Document for supportive care guidelines, including use of corticosteroids.

This document is confidential and the property of the University of Pennsylvania. No part of it may be transmitted, reproduced, published, or used by other persons without prior written authorization from the regulatory sponsor.

Table 3 Dose modification and toxicity management guidelines for immune-related AEs associated with pembrolizumab

General instructions:				

 1. Corticosteroid taper should be initiated upon AE improving to Grade 1 or less and continue to taper over at least 4 weeks. 2. For situations where pembrolizumab has been withheld, pembrolizumab can be resumed after AE has been reduced to Grade 1 or 0 and corticosteroid has been tapered. Pembrolizumab should be permanently discontinued if AE does not resolve within 12 weeks of last dose or corticosteroids cannot be reduced to ≤ 10 mg prednisone or equivalent per day within 12 weeks. 3. For severe and life-threatening irAEs, IV corticosteroid should be initiated first, followed by oral steroid. Other immunosuppressive treatment should be initiated if irAEs cannot be controlled by corticosteroids. 				
Immune-related AEs	Toxicity grade or conditions (CTCAEv5.0)	Action taken to pembrolizumab	irAE management with corticosteroid and/or other therapies	Monitor and follow-up
Pneumonitis	Grade 2	Withhold	
 • Administer corticosteroids (initial dose of 1-2 mg/kg prednisone or equivalent) followed by taper 	
 • Monitor participants for signs and symptoms of pneumonitis • Evaluate participants with suspected pneumonitis with radiographic imaging and initiate corticosteroid treatment • Add prophylactic antibiotics for opportunistic infections
	Grade 3 or 4, or recurrent Grade 2	Permanently discontinue		

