Diarrhea / Colitis	Grade 2 or 3	Withhold	
 • Administer corticosteroids (initial dose of 1-2 mg/kg prednisone or equivalent) followed by taper 	
 • Monitor participants for signs and symptoms of enterocolitis (ie, diarrhea, abdominal pain, blood or mucus in stool with or without fever) and of bowel perforation (ie, peritoneal signs and ileus).

This document is confidential and the property of the University of Pennsylvania. No part of it may be transmitted, reproduced, published, or used by other persons without prior written authorization from the regulatory sponsor.

	Grade 4	Permanently discontinue		
 Participants with \geq Grade 2 diarrhea suspecting colitis should consider GI consultation and performing endoscopy to rule out colitis. Participants with diarrhea/colitis should be advised to drink liberal quantities of clear fluids. If sufficient oral fluid intake is not feasible, fluid and electrolytes should be substituted via IV infusion.
AST / ALT elevation or Increased bilirubin	Grade 2	Withhold ¹	
 Administer corticosteroids (initial dose of 0.5- 1 mg/kg prednisone or equivalent) followed by taper 	
 Monitor with liver function tests (consider weekly or more frequently until liver enzyme value returned to baseline or is stable)
	Grade 3 or 4	Permanently discontinue ¹	
 Administer corticosteroids (initial dose of 1-2 mg/kg prednisone or equivalent) followed by taper 	
Type 1 diabetes mellitus (T1DM) or Hyperglycemia	Newly onset T1DM or Grade 3 or 4 hyperglycemia associated with evidence of β -cell failure	Withhold	
 Initiate insulin replacement therapy for participants with T1DM Administer anti-hyperglycemic in participants with hyperglycemia 	
 Monitor participants for hyperglycemia or other signs and symptoms of diabetes.
Hypophysitis	Grade 2	Withhold	
 Administer corticosteroids and initiate hormonal replacements as clinically indicated. 	
 Monitor for signs and symptoms of hypophysitis (including hypopituitarism and adrenal insufficiency)
	Grade 3 or 4	Withhold or permanently discontinue ²		

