Hyperthyroidism	Grade 2	Continue	
 Treat with non-selective beta-blockers (eg, propranolol) or thionamides as appropriate 	
 Monitor for signs and symptoms of thyroid disorders.
	Grade 3 or 4	Withhold or permanently discontinue ²		

This document is confidential and the property of the University of Pennsylvania. No part of it may be transmitted, reproduced, published, or used by other persons without prior written authorization from the regulatory sponsor.

Hypothyroidism	Grade 2-4	Continue	
 Initiate thyroid replacement hormones (eg, levothyroxine or liothyronine) per standard of care 	
 Monitor for signs and symptoms of thyroid disorders.
Nephritis and Renal dysfunction	Grade 2	Withhold	
 Administer corticosteroids (prednisone 1-2 mg/kg or equivalent) followed by taper. 	
 Monitor changes of renal function
	Grade 3 or 4	Permanently discontinue		
Myocarditis	Grade 1 or 2	Withhold	
 Based on severity of AE administer corticosteroids 	
 Ensure adequate evaluation to confirm etiology and/or exclude other causes
	Grade 3 or 4	Permanently discontinue		
All other immune-related AEs ³	Intolerable/persistent Grade 2	Withhold	
 Based on type and severity of AE administer corticosteroids 	
 Ensure adequate evaluation to confirm etiology and/or exclude other causes
	Grade 3	Withhold or discontinue based on the type of event. Events that require discontinuation include and not limited to: Gullain-Barre Syndrome, encephalitis		
	Grade 4 or recurrent Grade 3	Permanently discontinue		

¹ For patients with liver metastasis who begin treatment with Grade 2 AST or ALT, if AST or ALT increases by greater than or equal to 50% relative to baseline and lasts for at least 1 week then patients should be discontinued.
 
² Withhold or permanently discontinue pembrolizumab is at the discretion of the investigator or treating physician.
				

This document is confidential and the property of the University of Pennsylvania. No part of it may be transmitted, reproduced, published, or used by other persons without prior written authorization from the regulatory sponsor.

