³“All other immune-related AEs” excludes hematologic AEs given that hematologic changes are not considered reportable AEs or treatment-limiting toxicity (Section 7.3, Section 8.1). For grade 3-4 hematologic toxicity at least possibly related to therapy, therapy will be held until toxicity resolves to grade 0-1 or subject’s baseline.

NOTE:

For participants with Grade 3 or 4 immune-related endocrinopathy where withhold of pembrolizumab is required, pembrolizumab may be resumed when AE resolves to \leq Grade 2 and is controlled with hormonal replacement therapy or achieved metabolic control (in case of T1DM).

This document is confidential and the property of the University of Pennsylvania. No part of it may be transmitted, reproduced, published, or used by other persons without prior written authorization from the regulatory sponsor.

Dose modification for cytokine release syndrome:

If patients develop cytokine release syndrome grades 1-3 after pembrolizumab, then pembrolizumab will be held until cytokine release syndrome resolves. Once cytokine release syndrome has fully resolved, the clinical investigator has the option of restarting pembrolizumab at ½ dose (100mg) every 3 weeks. If patients develop grade 4 cytokine release syndrome or require administration of tocilizumab, pembrolizumab will be stopped due to drug toxicity.

Dosing interruptions are permitted in the case of medical / surgical events or logistical reasons not related to study therapy (e.g., elective surgery, unrelated medical events, patient vacation, and/or holidays). Subjects should be placed back on study therapy within 3 weeks of the scheduled interruption, unless otherwise discussed with the Principal Investigator and the Data and Safety Monitoring Board. The reason for interruption should be documented in the patient's study record.

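### Table 3 sets a stricter resumption rule for Grade 2 hypophysitis than for Grade 3 or 4 hypophysitis, and the plan does not settle whether a resulting Grade 2 discontinuation counts in the primary safety endpoint

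*Combined protocol and SAP*

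**What the plan says.** All the treatment rules at issue are in Section 5.2.1.2, Table 3.

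- **General instruction 2, resumption.** After a hold, "pembrolizumab can be resumed after AE has been reduced to Grade 1 or 0 and corticosteroid has been tapered".
- **General instruction 2, 12-week rule.** "Pembrolizumab should be permanently discontinued if AE does not resolve within 12 weeks of last dose". The same instruction also calls for discontinuation if the steroid dose cannot be brought down in that time.
- **Hypophysitis row.** "Hypophysitis Grade 2 Withhold". Grade 3 or 4 is withhold or permanently discontinue, and footnote 2 says the choice "Withhold or permanently discontinue pembrolizumab is at the discretion of the investigator or treating physician". Management is "Administer corticosteroids and initiate hormonal replacements as clinically indicated".
- **Thyroid rows.** "Hyperthyroidism Grade 2 Continue" and "Hypothyroidism Grade 2-4 Continue".
- **Type 1 diabetes row.** New-onset disease is withheld with no grade attached; hyperglycemia is withheld at Grade 3 or 4 with evidence of beta-cell failure.
- **NOTE after the table.** "For participants with Grade 3 or 4 immune-related endocrinopathy where withhold of pembrolizumab is required, pembrolizumab may be resumed when AE resolves to" Grade 2 or lower and is controlled on hormone replacement, or has reached metabolic control in type 1 diabetes.

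The primary safety criterion appears in several forms. The synopsis (Section 1.0) and the hypothesis (Section 3.1) require that at most 30% of patients have toxicity resulting in discontinuation, with no minimum grade. Section 8.1.1 defines success as the absence of an at least possibly related event leading to permanent discontinuation, and defines the monitored failure rate, FR, as the rate of discontinuation. The same section then defines toxicity failures as Grade 3 or higher non-hematologic toxicity with permanent discontinuation, or any related Grade 4 non-hematologic toxicity or cytokine release syndrome.

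**The concern.** The endocrinopathy NOTE recognises that an event can settle at Grade 2 on replacement and still be compatible with further treatment. It grants this only to patients whose event reached Grade 3 or 4. A patient withheld for hypophysitis that never rose above Grade 2 falls back on general instruction 2, which asks for Grade 0 or 1 and carries the 12-week rule. The resumption rule is therefore more restrictive for the milder course of the same event.

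This bears on the statistics because discontinuation for toxicity is the primary safety measure in a 12-patient trial. If Table 3 directs a discontinuation after a Grade 2 event and permits resumption after a Grade 3 event that ends in the same state, part of the endpoint reflects how the table is drafted. The plan's definitions also disagree on whether the Grade 2 discontinuation counts at all.

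**Working it through.** **Step 1. Two hypophysitis patients in the same final state (Grade 2, controlled on replacement).**

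| | Patient A: peak Grade 2 | Patient B: peak Grade 3 or 4, held |
|---|---|---|
| Action at peak (Table 3) | Withhold | Withhold, or permanently discontinue at discretion |
| Governing resumption text | General instruction 2 | NOTE |
| Grade needed to resume | 0 or 1 | 2 or lower, controlled |
| May resume in this state? | No | Yes |
| If the state persists | 12-week rule, if the event counts as not resolved | Already eligible to resume |

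**Step 2. How far this reaches.** Hypophysitis is the only named endocrine row that explicitly withholds at Grade 2. Grade 2 hyperthyroidism and Grade 2 to 4 hypothyroidism continue treatment, so no resumption rule is triggered. Unlisted endocrinopathies could enter through the intolerable or persistent Grade 2 line of the all-other row. For new-onset type 1 diabetes, the NOTE mentions metabolic control but is addressed to Grade 3 or 4 events, and the row gives no grade. Whether the NOTE applies there is unclear.

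**Step 3. Classification under each endpoint wording.**

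| Course | Synopsis, hypothesis, success, FR | Toxicity-failure sentence |
|---|---|---|
| Grade 2, permanently discontinued | Failure | Not a failure |
| Grade 3, resumed at Grade 2 | Not a failure | Not a failure |
| Grade 4, resumed at Grade 2 | Not a failure | Failure |

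The table takes each event as at least possibly related to pembrolizumab. The severity reversal carries into the endpoint under the first column only. Under the second, the Grade 2 case drops out and a resumed Grade 4 event counts.

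**Step 4. Size at n = 12.** The plan gives no figure for this point, so there is none to reproduce.

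- One patient: 1/12 = 8.3 percentage points.
- 3/12 = 25.0%, which meets the 30% criterion; 4/12 = 33.3%, which does not.
- With the plan's Beta(1,1) prior, 3/12 gives Beta(1+3, 1+9) = Beta(4,10) and Pr[FR > 0.30] = 0.421. For 4/12, Beta(5,9) gives 0.654. Both are far below the 0.975 stopping threshold.

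**Step 5. How often one patient would be decisive.** The result turns on this patient only if exactly 3 of the other 11 are failures. For a per-patient failure rate p, that probability is C(11,3) × p³ × (1−p)⁸, with C(11,3) = 165.

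| p | Source | Probability |
|---|---|---|
| 0.026 | Lung-cancer rate, Section 4.2.3.1 | 0.2% |
| 0.042 | Melanoma rate, Section 4.2.3.1 | 0.9% |
| 0.10 | Assumed | 7.1% |
| 0.20 | Assumed | 22.1% |
| 0.30 | Assumed | 25.7% |

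These figures are conditional on such a patient occurring. The documents do not say how often that would be.

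**The case against.** **The endpoint effect depends on the definition.** A reader might infer that a milder event necessarily produces a primary-endpoint failure. The documents do not support that, because the toxicity-failure sentence in Section 8.1.1 excludes Grade 2 discontinuations. This objection stands and limits the claim.

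**The wording is softer than a mandate.** Instruction 2 says *can* and *should*, and it does not tie *resolve* to a grade. An investigator could regard an endocrinopathy controlled on replacement as resolved for the 12-week rule. It is therefore too strong to say that the Grade 2 patient must be discontinued at 12 weeks. Section 5.6 does list unacceptable adverse experiences as described in Section 5.2.1.2 among the reasons for mandatory discontinuation, so the softer wording does not settle the matter. The resumption threshold of Grade 0 or 1 is explicit in either case.

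**The severe course is not exempt.** Footnote 2 leaves permanent discontinuation open for Grade 3 or 4 hypophysitis. Resumption is permitted there and not guaranteed. This is correct.

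**Scope.** A reader might extend the inversion to all endocrinopathies, to type 1 diabetes, or to Grade 1 myocarditis, where the hold begins at a grade that already satisfies instruction 2. The thyroid rows rule out the first. For diabetes the text is unclear, and an inversion is not shown. For myocarditis, release also depends on the steroid taper, and the row requires evaluation of the cause, so an empty hold is not shown.

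**Another document may help.** Section 12.4 says an Events of Clinical Interest guidance document will guide administration and discontinuation. It is not reproduced in the text available for this review and might address Grade 2 endocrinopathy. The contradiction within Table 3 would remain and would still need reconciling with that guidance.

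**The arithmetic is generic.** Any one-patient classification question at n = 12 is worth 8.3 points. That is so, and the calculation supports only a marginal effect.

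**Conclusion.** Table 3 is internally inconsistent for hypophysitis. On its literal wording, a patient held at Grade 2 faces a stricter resumption threshold than one held at Grade 3 or 4 who has reached the same controlled Grade 2 state. The same could hold for unlisted endocrinopathies held as intolerable or persistent Grade 2, and new-onset type 1 diabetes is left unclear.

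The effect on the primary endpoint is conditional on three things: that a Grade 2 case controlled on replacement is treated as not resolved and discontinued; that the synopsis, hypothesis, success and FR wording governs over the toxicity-failure sentence; and, for the 30% verdict to change, that exactly 3 of the other 11 patients are failures. If all three hold, one patient moves the result from 25.0% to 33.3%. At that margin the stopping rule is not triggered either way. This is a narrow inconsistency, inexpensive to correct, and it also exposes an unresolved conflict between the failure definitions.

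**What to change.** 1. Reconcile general instruction 2, the hypophysitis and type 1 diabetes rows and the NOTE in Table 3 with one another, and check them against the Events of Clinical Interest guidance document. The clinical team decides the thresholds.
2. State whether an endocrinopathy controlled on hormone replacement counts as not resolved under the 12-week rule.
3. State whether a permanent discontinuation for Grade 2 toxicity is a failure. Use one definition in Sections 1.0, 3.1 and 8.1.1, covering the success definition, the toxicity-failure sentence and FR.

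The cost is a protocol wording amendment. It needs no added patients, visits or procedures. If patients have already been classified, their discontinuations should be reviewed once against the single definition.

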5.2.2 Timing of Dose Administration

Trial treatment should be administered on Day 1 of each cycle after all procedures/assessments have been completed as detailed on the Trial Flow Chart (Section 6.0). Trial treatment may be administered up to 3 days before or 3 days after the scheduled Day 1 of each cycle due to administrative reasons.

All trial treatments will be administered on an outpatient basis.

Pembrolizumab 200 mg will be administered as a 30 minute IV infusion every 3 weeks. Sites should make every effort to target infusion timing to be as close to 30 minutes as possible. However, given the variability of infusion pumps from site to site, a window of -5 minutes and +10 minutes is permitted (i.e., infusion time is 30 minutes: -5 min/+10 min).

The Pharmacy Manual contains specific instructions for the preparation of pembrolizumab infusion fluid and administration of infusion solution.

This document is confidential and the property of the University of Pennsylvania. No part of it may be transmitted, reproduced, published, or used by other persons without prior written authorization from the regulatory sponsor.

5.2.3 Trial Blinding/Masking

This is an open-label trial; therefore, the Sponsor, investigator and subject will know the treatment administered.

5.3 Concomitant Medications/Vaccinations (allowed & prohibited)

Medications or vaccinations specifically prohibited in the exclusion criteria are not allowed during the ongoing trial. If there is a clinical indication for one of these or other medications or vaccinations specifically prohibited during the trial, discontinuation from trial therapy or vaccination may be required. The investigator should discuss any questions regarding this with the Principal Investigator. The final decision on any supportive therapy or vaccination rests with the investigator and/or the subject's primary physician.

5.3.1 Acceptable Concomitant Medications

All treatments that the investigator considers necessary for a subject's welfare may be administered at the discretion of the investigator in keeping with the community standards of medical care. All concomitant medications will be recorded on the case report form (CRF) including all prescription, over-the-counter (OTC), herbal supplements, and IV medications and fluids. If changes occur during the trial period, documentation of drug dosage, frequency, route, and date may also be included on the CRF.

All concomitant medications received within 28 days before the first dose of trial treatment and 30 days after the last dose of trial treatment should be recorded. Concomitant medications administered after 30 days after the last dose of trial treatment should be recorded for SAEs and ECIs as defined in Section 7.2 and 7.3.

5.3.2 Prohibited Concomitant Medications

Subjects are prohibited from receiving the following therapies during the Screening and Treatment Phase (including retreatment for post-complete response relapse) of this trial:

- Antineoplastic systemic chemotherapy or biological therapy
- Immunotherapy not specified in this protocol

This document is confidential and the property of the University of Pennsylvania. No part of it may be transmitted, reproduced, published, or used by other persons without prior written authorization from the regulatory sponsor.

- Chemotherapy not specified in this protocol
- Investigational agents other than pembrolizumab
- Radiation therapy
 - Note: Radiation therapy to a symptomatic solitary lesion or to the brain may be allowed at the investigator's discretion.
- Live vaccines within 30 days prior to the first dose of trial treatment and while participating in the trial. Examples of live vaccines include, but are not limited to, the following: measles, mumps, rubella, varicella/zoster, yellow fever, rabies, BCG, and typhoid vaccine.
- Systemic glucocorticoids for any purpose other than to modulate symptoms from an event of clinical interest of suspected immunologic etiology. The use of physiologic doses of corticosteroids may be used for adrenal insufficiency, treatment of shock, or for other indications approved after consultation with the Principal Investigator.
- *Note: Hematopoietic growth factors, including G-CSF and EPO, are permitted*

Subjects who, in the assessment by the investigator, require the use of any of the aforementioned treatments for clinical management should be removed from the trial. Subjects may receive other medications that the investigator deems to be medically necessary.

The Exclusion Criteria describes other medications which are prohibited in this trial.

There are no prohibited therapies during the Post-Treatment Follow-up Phase.

5.4 Rescue Medications & Supportive Care

5.4.1 Supportive Care Guidelines

Subjects should receive appropriate supportive care measures as deemed necessary by the treating investigator. Suggested supportive care measures for the management of adverse events with potential immunologic etiology are outlined below and in greater detail in the ECI guidance document. Where appropriate, these guidelines include the use of oral or intravenous treatment with corticosteroids as

This document is confidential and the property of the University of Pennsylvania. No part of it may be transmitted, reproduced, published, or used by other persons without prior written authorization from the regulatory sponsor.

well as additional anti-inflammatory agents if symptoms do not improve with administration of corticosteroids. Note that several courses of steroid tapering may be necessary as symptoms may worsen when the steroid dose is decreased. For each disorder, attempts should be made to rule out other causes such as metastatic disease or bacterial or viral infection, which might require additional supportive care. The treatment guidelines are intended to be applied when the investigator determines the events to be related to pembrolizumab.

Note: if after the evaluation the event is determined not to be related, the investigator is instructed to follow the ECI reporting guidance but does not need to follow the treatment guidance (as outlined in the ECI guidance document). Refer to Section 5.2.1.2 for dose modification.

Management of Infusion Related Reactions: Signs and symptoms usually develop during or shortly after drug infusion and generally resolve completely within 24 hours of completion of infusion.

Table

~~Table~~ 4 below shows treatment guidelines for subjects who experience an infusion reaction associated with administration of pembrolizumab.

Table 4 Infusion Reaction Treatment Guidelines

NCI CTCAE Grade	Treatment	Premedication at subsequent dosing
Grade 1 Mild transient reaction; infusion interruption not indicated; intervention not indicated	Increase monitoring of vital signs as medically indicated until the subject is deemed medically stable in the opinion of the investigator.	None
Grade 2 Therapy or infusion interruption indicated but responds promptly to symptomatic treatment (e.g., antihistamines, NSAIDS, narcotics, IV fluids); prophylactic medications indicated for <=24 hrs	Stop Infusion and monitor symptoms. Additional appropriate medical therapy may include but is not limited to: IV fluids Antihistamines NSAIDS Acetaminophen Narcotics	Subject may be premedicated 1.5h (± 30 minutes) prior to infusion of pembrolizumab with, but is not limited to: Diphenhydramine 50 mg po (or equivalent dose of antihistamine).

This document is confidential and the property of the University of Pennsylvania. No part of it may be transmitted, reproduced, published, or used by other persons without prior written authorization from the regulatory sponsor.

NCI CTCAE Grade	Treatment	Premedication at subsequent dosing
	
Corticosteroids
 
Increase monitoring of vital signs as medically indicated until the subject is deemed medically stable in the opinion of the investigator.
 
If symptoms resolve within one hour of stopping drug infusion, the infusion may be restarted at 50% of the original infusion rate (e.g., from 100 mL/hr to 50 mL/hr).
 
Otherwise dosing will be held until symptoms resolve and the subject should be premedicated for the next scheduled dose.
 
Participants who develop Grade 2 toxicity despite adequate premedication should be permanently discontinued from further trial treatment administration.
	
Acetaminophen 500-1000 mg po (or equivalent dose of antipyretic).


Grades 3 or 4
 
Grade 3: Prolonged (e.g., not rapidly responsive to symptomatic medication and/or brief interruption of infusion); recurrence of symptoms following initial improvement; hospitalization indicated for clinical sequelae (e.g., renal impairment, pulmonary infiltrates)
 
Grade 4: Life-threatening consequences; urgent intervention indicated
	
Stop Infusion.
 
Additional appropriate medical therapy may include but is not limited to:
 
 IV fluids Antihistamines NSAIDS Acetaminophen Narcotics Oxygen Pressors Corticosteroids Epinephrine** 
Increase monitoring of vital signs as medically indicated until the subject is deemed medically stable in the opinion of the investigator. Hospitalization may be indicated.
 
**In cases of anaphylaxis, epinephrine should be used immediately
 
Participant is permanently discontinued from further further study drug treatment.
	
No subsequent dosing

Appropriate resuscitation equipment should be available in the room and a physician readily available during the period of drug administration.
		

This document is confidential and the property of the University of Pennsylvania. No part of it may be transmitted, reproduced, published, or used by other persons without prior written authorization from the regulatory sponsor.

NCI CTCAE Grade	Treatment	Premedication at subsequent dosing
For further information, please refer to the Common Terminology Criteria for Adverse Events v5 (CTCAE)		

